#### 7.1.2 Analysis

A one-tailed paired t-test will be used to test if the number of manual checks has been reduced relative to week 1. If the variable is not normally distributed the non-parametric Wilcoxon signed-rank test will be used and in case of a significant result, a one-sided 95% confidence interval will be constructed for the percentage change in checks between week 1 and week 3 to validate at least a 30% reduction. The Shapiro-Wilk test will be used to test normality.

### 7.2 Secondary Efficacy Endpoints

- Change in the number of leakages into the clothes and/or bed linen at week 3 (investigational week) compared to week 1 (baseline week).

A paired t-test will be used for comparison. If the variable is not normally distributed a non-parametric Wilcoxon signed rank test will be used.

- Evaluate change in skin redness and irritation, at week 3 (investigational week) compared to week 1 (baseline week).

This endpoint will be evaluated using the Ghent Global IAD Categorisation Tool (GLOBIAD) (Ref 3.). GLOBIAD is a categorisation tool to monitor Incontinence associated dermatitis (IAD) prevalence and incidence. IADs can be scored as 1A, 1B, 2A and 2B. The analysis is to determine if there is a significant difference in scoring between the two time points. A paired t-test will be used for comparison. If the variable is not normally distributed a non-parametric Wilcoxon signed rank test will be used.

- Evaluate the number of fecal incidences.

	
Title: Statistical Analysis Plan
	
Id: Version 2.0_25-Nov-2021

---	---	------------------------------------

A non-parametric Wilcoxon signed rank test will be used for comparison.

- Evaluate usability
- Descriptive and summary statistics

The Shapiro-Wilk test will be used to test normality where appropriate.

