At visit 1, the following assessments/procedures will be performed for those who did not need to attend Visit 0:

- Day 0
- Performed by investigator and designated nurse. CGR, informed consent witness, and DEU visit site, or investigator and nurse visit DEU's home.
- Informed consent DEU and witness as applicable.
- Informed consent CGR.
- Eligibility verification (DEU and CGR).
- Demography (DEU and CGR).
- Medical and surgical history (DEU).
- Relevant concomitant medication (DEU).
- Evaluation of general cognitive function (DEU).
- Physical examination (DEU).
- Skin redness/irritation assessment (DEU).
- Pregnancy test (DEU with childbearing potential).

- Instruction and handover of baseline week diary.
- Instruction and handover of single-use TENA incontinence products.
- Scheduling of visit 2.

At visit 1, the following assessments/procedures will be performed for those who completed visit 0:

- Day 0 (+1-3 days)
- Instruction and handover of baseline week diary.
- Handover of single-use TENA incontinence products.
- Relevant concomitant medication review (DEU).
- Skin redness/irritation assessment (DEU).
- Scheduling of visit 2.

Baseline registrations are to be initiated on the first day following the enrollment, i.e. day 1. If required, additional support will be provided as needed during the course of the clinical investigation.

Visit 2: Initiate baseline week.

- Day 1 (+1-3 days)
- Performed by designated nurse in DEU's home, over phone or video call.
- Confirmation of correct baseline week diary initiation.
- Concomitant medication review (DEU).
- Scheduling of visit 3.

Visit 3: Initiate learning week.

- Day 8 (+1-3 days).
- Performed by designated nurse in DEU's home.
- Confirmation of correct baseline week diary registration.
- Concomitant medication review (DEU).
- Skin redness/irritation assessment (DEU).
- Documentation of AE/ADE (DEU and CGR).
- Handover of TENA SmartCare Change Indicator (including instruction/training/verification of understanding).
- Instruction and handover of learning week diary.
- Handover of single use TENA incontinence products.
- Scheduling of Visit 4/5, as applicable.

Visit 4: Assure correct learning and use as intended (optional visit)

- 1-3 days post visit 3.
- Performed by designated nurse, as required based on need for additional support, e.g. visit/phone call/video call.

In case the visit is conducted the following will be investigated:

- Confirmation of correct learning week diary registration.

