10.5.1.4 Visit 3 (Day 8 (+ 1-3 days))

Visit 3 is conducted by the designated nurse in the DEU's home. Correctness of baseline week diary registrations will be confirmed. Visual assessment and GLOBIAD scoring of skin redness/irritation in the body region covered by the absorbing incontinence product will be performed on the DEU. All AEs/ADEs and/or DDs will be documented and followed-up. The TENA SmartCare Change Indication (sensor and app) and applicable instruction (IFU), learning week diary, and additional single use TENA incontinence products will be provided.

Before completion of visit 3, the designated nurse shall assure that the CGR understands how to install and use the investigational product.

At visit 3, the following assessment/procedures will be performed:

- Confirmation of correct baseline week diary registration.
- Concomitant medication review (DEU).
- Skin redness/irritation assessment (DEU).
- Documentation of AE/ADE (DEU and CGR).

	Title: POWER Clinical Investigation Plan	Id:
---	---	-----

- Handover of TENA SmartCare Change Indicator (including instruction/training/verification of understanding).
- Instruction and handover of learning week diary.
- Handover of single use TENA incontinence products.
- Scheduling of Visit 4/5, as applicable.

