10.5.1.8 Visit 7 (≥ 7 completed days post Visit 5)

Visit 7 is conducted by the investigator and nurse in the DEU's home or at site. Correctness of investigational week diary registrations and applicable questionnaires filled in by the CGR, will be confirmed. Visual assessment and GLOBIAD scoring of skin redness/irritation in the body region covered by the absorbing incontinence product will be performed on the DEU. All AEs/ADEs and/or DDs will be documented and followed-up, as applicable. After completion of visit 7 the DEU and CGR will finish the clinical investigation.

At visit 7, the following assessment/procedures will be performed:

- Confirmation of correct investigational week diary registration.
- Concomitant medication review (DEU).
- Skin redness/irritation assessment (DEU).
- Documentation of AEs/ADEs (DEU and CGR) and DDs, or follow-up as applicable.
- Finalization of study period.
- Collection of investigational products.
- Pregnancy test (DEU with childbearing potential).
- Questionnaire completion (CGR);
 - o Whether the TENA SmartCare Change Indicator facilitates the decision to change the TENA incontinence product
 - o Likelihood of continued use of the TENA SmartCare Change Indicator.
 - o Usability

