10.5.3 Performance Variables and Measurements

10.5.3.1 Diary completion

Three different diaries will be filled out and completed by the CGR; Baseline diary, learning week diary, and investigational week diary. Number of manual checks in-between the daily changes of the absorbing incontinence product are to be documented continuously throughout the day. The investigational week diary will be compared to the baseline week diary.

The following data will be documented in the diary:

- Number of manual checks in-between the daily changes of the absorbing incontinence product
- Leakage into clothes and/or bed linen
- Fecal incidences
- Concomitant medication

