#### **4.6 Multiple Comparisons/Multiplicity**

No adjustment for multiplicity of testing will be done. There will be one formal statistical analysis (primary efficacy endpoint) in line with the sample size determination. All other statistical tests will be considered as descriptive.

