#### **4.7 Handling of Drop-outs, Missing Data and Outliers**

Outliers will be included in summary tables and listings, and will not be handled separately. Available data from prematurely withdrawn subjects will be included in the analysis as far as possible. Missing data will not be imputed.

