### 7.1 Primary efficacy endpoint

#### 7.1.1 Definition

The primary efficacy endpoint is the change in percentage of the number of manual checks between week 1 and week 3 of the investigation. The average manual checks/day for a subject week will be used for the percentage calculation, since data may be available for less or more than 7 days.

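### SAP 7.2 compares leakage counts with no denominator, although SAP 7.1.1 averages checks from the same diary per day; if average diary lengths differ between the two weeks, the leakage change is biased

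*SAP*

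**What the plan says.** SAP 7.2 defines the leakage endpoint as "Change in the number of leakages into the clothes and/or bed linen at week 3 (investigational week) compared to week 1 (baseline week)". It is compared by a paired t-test, or by a Wilcoxon signed-rank test if normality fails. Protocol 12.1 also speaks only of the change in the number of leakages. Neither place gives a per-day or per-week basis, a fixed 7-day window or a rule for incomplete diaries.

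For manual checks, SAP 7.1.1 uses the average per day within a subject week, "since data may be available for less or more than 7 days". Protocol 10.5.3.1 lists "Leakage into clothes and/or bed linen" among the items in the same diary as the checks.

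The diary periods are bounded by visits:

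- **Baseline:** "Baseline registrations are to be initiated on the first day following the enrollment, i.e. day 1" (Protocol synopsis). Visit 3 closes the period at Day 8, with 1 to 3 further days allowed (Protocol 10.5.1.4).
- **Investigational week:** it starts at Visit 5 and ends at Visit 7, at least 7 completed days later, with no upper limit (Protocol 10.5.1.8).

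SAP 4.7 adds: "Available data from prematurely withdrawn subjects will be included in the analysis as far as possible". Missing data are not imputed. On the status of the test, SAP 4.6 says: "All other statistical tests will be considered as descriptive".

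For fecal incidences, Protocol 12.1 specifies a weekly figure. SAP 7.2 omits that unit, and SAP 8 declares no changes from the protocol.

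**The concern.** The SAP recognises that diaries will not all cover 7 days and corrects for it, but only for the primary endpoint. A longer diary collects more leakages even if nothing about the patient or the device has changed. Pairing within subject does not remove this, because the two diaries of one subject can differ in length.

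Fewer leakages is an anticipated benefit of the device (Protocol 8.1) and evaluating leakage is a secondary objective (Protocol 9.2). The results feed the Clinical Evaluation Report. A leakage change that partly reflects visit scheduling would be reported with a p-value, and it could flatter the device or count against it. In an open single-arm study, leaving the unit unstated also lets the choice between counts and rates be made after the data are seen.

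**Working it through.** **The plan's own figures.** The documents give no leakage rate, no variance and no power for this endpoint. The only figure used here is the 24 evaluable subjects (SAP 4.1). The enrolment target follows from it: 24 / (1 − 0.30) = 34.3, rounded up to 35, as stated.

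**Diary lengths allowed.** Baseline runs from day 1 up to Visit 3 on day 8 to day 11, which is 7 to 10 days. Week 3 is at least 7 days with no maximum. A subject who withdraws during week 3 contributes fewer.

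**Expected change with no true effect.** Let a subject's leakage rate be constant at r per day, with diary lengths L1 (baseline) and L3 (week 3).

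- Expected change in the count: r × (L3 − L1).
- Relative change: L3/L1 − 1.
- Expected change per diary day: r − r = 0.

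| L1 (days) | L3 (days) | Spurious relative change |
|---|---|---|
| 10 | 7 | −30% |
| 8 | 7 | −12.5% |
| 7 | 5 (truncated week 3) | −28.6% |
| 7 | 8 | +14.3% |
| 7 | 10 | +42.9% |

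If baseline is spread evenly over 7, 8, 9 and 10 days (mean 8.5) and week 3 is 7 days, the average change is 7/8.5 − 1 = −17.6%. The reverse gives 8.5/7 − 1 = +21.4%.

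**Effect on the test.** I simulated 24 subjects with Poisson leakages, gamma-distributed subject rates (shape 2), no true change and a two-sided paired t-test at 5%. There were 10,000 trials per scenario. The SAP does not state the sidedness of this test, so two-sided is assumed. Leakage rates and length distributions are also assumptions. Lengths are whole days, evenly spread over the range shown.

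| Baseline / week 3 (days) | 1 leak per week | 0.3 per day | 0.5 per day | 1 per day |
|---|---|---|---|---|
| 7–10 / 7, counts | 9.4% | 14.8% | 21.2% | 37.2% |
| 7 / 7–10, counts | 9.6% | 15.6% | 21.8% | 37.3% |
| 7–8 / 7, counts | 5.2% | 6.0% | 7.0% | 8.6% |
| 7–10 / 7–10, counts | 5.2% | 4.8% | 5.0% | 4.6% |

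With leakages per diary day, the false-positive rate is 4.4% to 5.1% across these scenarios.

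Using the planned rule (Shapiro-Wilk, then t-test or Wilcoxon; 2,000 trials) changes little: 9.3%, 14.8%, 22.9% and 37.0% for 7–10 / 7, and 4.5% to 5.8% when both periods run 7–10 days.

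**The case against.** Five points can be made against this.

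1. **Average lengths must differ.** Differences that balance out across subjects add noise but no bias. This is correct, and the 7–10 / 7–10 row shows it.

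2. **The larger error rates need one period to stretch while the other stays at exactly 7 days.** Both windows allow extra days, so milder imbalance is plausible. With baseline 7–10 and week 3 7–9 days, the spurious change is 8/8.5 − 1 = −6%. With 80% of baselines at exactly 7 days, the rest spread over 8–10 and week 3 at 7, it is 7/7.4 − 1 = −5%. In both cases the false-positive rate is about 5% to 8%. So the size is uncertain and may be small. The documents do not exclude the larger case.

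3. **The only open-ended window is week 3, and a longer week 3 works against the device.** With baseline 7 and week 3 7–10 days, a spurious significant reduction appears in under 0.5% of trials. A spurious benefit needs longer baselines or truncated week-3 diaries. Both are possible under the plan, and bias against the device is still bias.

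4. **Week 1 and week 3 could mean exactly 7 days, with scheduling days left outside.** Protocol 10.1 can be read that way. But no section truncates either diary, and SAP 7.1.1 says a subject week may hold fewer or more than 7 days.

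5. **The test is secondary and descriptive.** True, and the pass/fail criterion (Protocol 12.5) is untouched. The label does not correct a biased estimate, which will still be reported.

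The 7-to-10-day baseline range is also not certain for subjects who attended Visit 0. Their diary is handed over at Visit 1, which may fall 1 to 3 days late. If day numbers are fixed, their baseline could be as short as 4 days. The documents do not settle this, and it adds to the reasons for a per-day basis.

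**Conclusion.** The concern holds. Applied as written, SAP 7.2 compares counts over periods that the plan itself allows to differ in length, and it omits the conversion that SAP 7.1.1 applies to the same diary. The bias is L3/L1 − 1 at a constant daily rate: about −18% or +21% on average if only one period stretches evenly over 7–10 days, about −5% to −6% under milder imbalance, and zero if average lengths match. The corresponding false-positive rates run from nominal to about 37%, depending on leakage rates and diary lengths that the documents do not give.

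The omission itself is certain; its size is not. The primary endpoint and the pass/fail criterion are unaffected. What is at risk is the reported leakage change and its descriptive p-value. This should be corrected, but it does not threaten the trial's main conclusion.

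**What to change.** In SAP 7.2 and Protocol 12.1, define leakage for each subject and period as the average number per recorded diary day (multiplied by 7 if a weekly figure is wanted), following SAP 7.1.1, and apply the paired test to the change in that average. A pre-specified common 7-day window with a minimum number of valid days, or leakages per product change, would also remove the dependence on diary length. The per-day rule is simplest because the plan already uses it.

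As a side point, restore the weekly unit for fecal incidences in SAP 7.2 and compute it the same way. Protocol 12.1 already has the unit, so this is mainly editorial.

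The cost is one or two SAP sentences and one matching phrase in Protocol 12.1. The number of diary days is already needed for the primary endpoint, so data collection does not change.

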### 7.3 Secondary Endpoint / Safety Endpoint

Incidence of adverse events and device deficiencies; AEs, ADEs, SAEs, SADEs and DDs.

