10.1.2 Secondary Endpoints

- Incidence of adverse events during week 2 (learning week) and week 3 (investigational week); adverse events (AE), adverse device effects (ADE), serious adverse events (SAE), and serious adverse device effects (SADE), and device deficiency (DD).
- Change in the number of leakages into the clothes and/or bed linen at week 3 (investigational week) compared to week 1 (baseline week).
- Evaluate change in skin redness and irritation, at week 3 (investigational week) compared to week 1 (baseline week).
- Evaluate usability (questionnaire week 2 and 3).
- Evaluate the number of fecal incidences.

	Title: POWER Clinical Investigation Plan	Id:
---	---	-----

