10.5.1.1 Visit 0 (Day -7)

This visit will only be completed for subjects who have not previously used TENA incontinence products. During 7 days the subject and caregiver will develop familiarity with TENA Incontinence products to ensure representative data collection during baseline week and the remainder of the investigation. This will be the screening and baseline visit for these subjects.

The screening visit is conducted by the investigator and the designated nurse, either at the site or in the DEU's home, as considered most appropriate. The investigator will introduce the clinical investigation and explain the CIP, procedures and objectives to the potential DEU, his/her witnesses and the CGR (Note, the CGR can act as one of the DEU's witnesses. If so the CGR and one of the witnesses is the same person). The investigator will verbally inform about the investigation and provide written patient information describing the clinical investigation, potential discomforts, risks and benefits of participation. Potential DEUs, their witnesses, and their CGRs will be given adequate time for review of the patient information and time to discuss the investigation and ask questions to the investigator. Any queries that a potential DEU/witness/CGR may have regarding the investigation will be addressed appropriately by the investigator. Potential DEU and their CGR will be instructed that they are free to withdraw their consent and to discontinue their participation in the investigation at any time without prejudice. In case a DEU is considered unable to provide informed consent, e.g. due to intellectual challenges, a legally designated representative must be available and willing to provide informed consent on behalf of the subject. If the DEU and the CGR are willing to participate in the investigation, they need to sign and date the Informed Consent Form (ICF) together with the investigator who gave the verbal and written information. The original ICF will be retained in the Investigator Site File (ISF) and a copy provided to the DEU and CGR. The investigator must obtain written informed consent before any clinical investigation-related procedures are performed on the subject, for further details on the informed consent process please see section 18.

After written informed consent has been obtained the DEU and CGR are considered to be enrolled in the clinical investigation. The DEU be allocated to a unique subject identification number.

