19.2 Methods for discovering and documenting AE/ADE

All subjects will be carefully monitored for the occurrence of AEs throughout the clinical investigation, from enrollment to completion the clinical investigation. Events prior to enrollment will be considered medical history. The investigator will collect safety information using non-leading questions such as "have you experienced any new health problems or worsening of existing conditions?" Events directly observed or spontaneously volunteered by subjects will also be recorded throughout the clinical investigation.

Clearly related signs, symptoms and abnormal diagnostic procedure results should be grouped together and reported as a single diagnosis or syndrome whenever possible.

All AEs, including but not limited to events reported by the subject or reported in response to an open question by the PI or member of the investigation team, which fall into any of the previously defined definitions must be recorded as an AE in the CRF and should include the following information:

- Brief description of the event (diagnosis).
- Date of event onset (and time, if relevant).

	Title: POWER Clinical Investigation Plan	Id:
---	---	-----

- Date of event resolution (and time, if relevant).
- Severity.
- Seriousness.
- Causality assessment (i.e. relationship to medical device and/or procedure).
- Event treatment.
- Event outcome.

If the AE meets seriousness criteria it should be subject to expedited reporting as described in section 19.4.

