**7.3.3 Presentation**

**AE/ADE:**

The following summaries of AEs and SAEs will be given:

- Total number of AEs
- Total number of unique AEs
- Total number of unique, related AEs
- Total number (%) of subjects with at least one AE
- Total number (%) of subjects with at least one related AE
- Total number (%) which had AE as reason for premature discontinuation of study device

Severity, action taken, concomitant therapy started and subject outcome of the AEs will be given in data listings only. AEs, which were reason for premature discontinuation of study device, will be listed separately.

Depending on the number of AEs reported, the most frequently reported (e.g. in more than 5% of the patients) AEs might be summarized separately.

The total number of SAEs and patients with a least one SAE will always be given. Further summaries of SAEs depending on the number of SAEs observed.

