**8 CHANGES FROM THE CIP**

Not applicable, no changes made.

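### SAP 7.3 omits the week 2–3 window of the protocol's adverse-event endpoint, so all-cause AE and SAE figures would include events from before the device was handed over

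*SAP*

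**What the plan says.** Protocol 10.1.2, like the synopsis, gives the safety endpoint a period: "Incidence of adverse events during week 2 (learning week) and week 3 (investigational week"), covering AEs, ADEs, SAEs, SADEs and device deficiencies.

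SAP 7.3 names the same event types without a period: "Incidence of adverse events and device deficiencies; AEs, ADEs, SAEs, SADEs and DDs". The summaries in SAP 7.3.3 include "Total number (%) of subjects with at least one AE", again with no onset rule and no split by study period. SAP 4.2.1 and 4.2.4 base the safety tables on all consented subjects. SAP 8, on changes from the protocol, reads "Not applicable, no changes made".

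On collection, Protocol 19.2 has AEs monitored "from enrollment to completion the clinical investigation". Enrolment means signed consent: "After written informed consent has been obtained the DEU and CGR are considered to be enrolled in the clinical investigation" (Protocol 10.5.1.1, repeated in 10.5.1.2). The Change Indicator is first handed over at Visit 3 (Protocol 10.5.1.4 and Table 2).

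**The concern.** The protocol endpoint describes what happens while the device is in use. A programmer working from the SAP has no instruction to exclude events that began earlier, although such events will be in the database. The overall AE and SAE tables would then mix the baseline week with the device weeks. For subjects new to TENA products they would also include the familiarisation week. The result would be presented as the protocol's endpoint when it is a different quantity, under a statement that nothing was changed.

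The figures are to feed the device's Clinical Evaluation Report (Protocol 10.1). An overall AE incidence that partly reflects device-free time could be read there as the incidence during use of the device.

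**Working it through.** **1. Does anything in the SAP restore the window?**

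- SAP 7.3.1 refers to the protocol for details of the event categories, not for the counting period.
- SAP 7.3.3 has no treatment-emergent or onset rule.
- SAP 7.2 keeps the week 3 against week 1 wording for leakage and skin redness, so periods are stated for some endpoints but not for this one.
- The safety set has no device-use condition. Adding one would still leave device users' earlier events in the tables.

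Nothing restores it.

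**2. Device time, checked against the plan's own figure.** Visit 5 is 7 to 10 completed days after Visit 3, and Visit 7 is at least 7 completed days after Visit 5 (Protocol Table 2). Nominal device time is 7 + 7 = 14 days, which matches the 2 weeks of exposure in SAP 6.3. With a 10-day learning period it is 10 + 7 = 17 days.

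**3. Device-free time under AE collection.** Visit 3 is Day 8, with an allowance to Day 11.

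- Start at Visit 1 (Day 0): 8 days nominal, 11 at most.
- Start at Visit 0 (Day −7): 7 + 8 = 15 days nominal, 7 + 11 = 18 at most. The extra 7 days apply only to subjects new to TENA products: "During 7 days the subject and caregiver will develop familiarity with TENA Incontinence products".

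**4. Device-free share = device-free days / (device-free days + device days)**, with Visit 7 taken 7 days after Visit 5.

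| Start | Nominal | Lowest | Highest |
|---|---|---|---|
| Visit 1 | 8/(8+14) = 8/22 = 36% | 8/(8+17) = 32% | 11/(11+14) = 44% |
| Visit 0 | 15/(15+14) = 15/29 = 52% | 15/(15+17) = 47% | 18/(18+14) = 56% |

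Visit 1 may fall up to 3 days late for Visit 0 starters. If Visit 3 is then timed from the delayed Visit 1, device-free time reaches 10 + 11 = 21 days and the share 21/(21+14) = 60%. On the day numbers in Table 2 the upper figure is 56%.

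**5. What this could do to a percentage of subjects.** The documents give no background AE rate. As an illustration, assume a constant rate and a 14-day incidence p. Over d days the incidence is 1 − (1 − p)^(d/14).

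| True 14-day incidence | Reported over 22 days | Reported over 29 days |
|---|---|---|
| 5% | 7.7% | 10.1% |
| 10% | 15.3% | 19.6% |
| 20% | 29.6% | 37.0% |

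**6. Which rows change?** An event caused by the Change Indicator cannot precede its handover, so related-AE, ADE and SADE rows barely move. They are not wholly immune. Relatedness also covers study procedures (Protocol 19.2.2), and the ADE definition extends to a comparator that is a medical device. The rows that change are total AEs, subjects with any AE, and the corresponding SAE figures.

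**The case against.** The best defence is that silence is not a changed endpoint. The SAP says it elaborates the protocol and declares no changes, so the protocol window could be taken to govern. SAP 7.2 also drops the questionnaire weeks from the usability endpoint, which looks like abbreviation. The protocol itself is mixed: the safety objective (9.2) has no week limit and 10.5.4 documents all events over the whole investigation. The objective concerns device-related events, and SAP 7.3.3 reports related AEs separately. Safety is not tested, the pass/fail criterion concerns manual checks only, and an AE listing is a deliverable, so no event disappears.

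Much of this stands, and it limits the point to a minor one. It does not remove it. Collecting all events from enrolment is sound, but the endpoint in 10.1.2 is narrower than what is collected, and the SAP is where that selection should be written down. Two defensible readings of the SAP give different AE percentages.

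A reader might go further and infer that device-related harm would be overstated, or that the plan throws away a before-and-after comparison of AEs. The documents support neither. Related events are tabulated separately and largely arise after handover. The own-control comparison in Protocol 10.2 is of manual checks, and no contrast of AEs between periods is planned.

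The SAP cites protocol version A, and the version of the supplied protocol cannot be confirmed. The comparison here is with the supplied text.

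**Conclusion.** Wrong as written, and minor. The SAP's safety summary does not match the protocol's endpoint, and the difference is not declared. It affects all-cause AE and SAE counts and percentages.

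The device-free share of observation time is firm at the nominal schedule. The ranges depend on the visit windows and on Visit 7 falling 7 days after Visit 5. Visit 7 has no upper limit, and any delay lowers the shares. It would be tempting to say that a third to a half of tabulated AEs will pre-date the device, but that needs a constant AE rate and equal ascertainment. The documents give no rate, and scheduled AE documentation begins only at Visit 3, so earlier events may be picked up less completely.

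No test and no pass/fail decision turns on this.

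**What to change.** In SAP 7.3 and 7.3.3, state that the endpoint counts AEs, ADEs, SAEs, SADEs and device deficiencies with onset from device handover at Visit 3 to Visit 7. Report events with onset from consent to handover in a separate column, so that none are lost. If the sponsor prefers to count from consent, say so in SAP 8 as a change from Protocol 10.1.2, with the reason.

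The cost is a few lines of SAP text and one table column. Onset date is already recorded for every AE (Protocol 19.2), so no new data are needed.
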